18.7 Sample Size and Power Estimate for the Primary Efficacy Endpoints

18.7.1 Part I – Difference in the composite image quality score between Feraheme and Ablavar

Sample size and power estimates are based on data from an internal pilot analysis. Based on the average composite image quality scores of two independent readers, the mean image quality score was 25.62 with a standard deviation of 1.82 for the Feraheme-enhanced, ventilator-gated MUSIC-MRI group. The difference in the image quality scores between two readers was a mean of -1.96 with a standard deviation of 2.72. We expect the agreement between two independent readings will improve with consensus reading in cases with largely different image quality scores (4 or more absolute difference in the score).

Based on the above preliminary analyses, for the interim analysis, a sample size of 20 in each contrast agent group will achieve a power of 62% to detect a difference of 1.75 (7% reduction) in the composite image quality scores between the Ablavar group and the Feraheme group with an estimated standard deviation of 2.10 in each group and a significance level of 2.5%.

In the primary analysis, a sample size of 36 subjects will achieve a power of 90% to detect a difference of 1.75 (7% reduction) in composite image quality scores between the Ablavar group and the Feraheme group with an estimated standard deviation of 2.10 in each arm and a significance level of 2.5%. Taking into consideration missing data due to unusable image quality or incomplete studies, we plan to enroll 40 CHD subjects in each group (N=80).

18.7.2 Part II – Difference in the composite image quality score between ventilator-gated and self-gated MUSIC-MRI

The quality of self-gated images are expected to be of at least equal quality to ventilator-gated images with a larger standard deviation due to variation in the methods of respiratory motion gating. We choose the non-inferior margin (87) to ensure that the upper bound of the 95% confidence interval (CI) for the difference between ventilator-gated and self-gated (ventilator – self-gated) is less than 1.75. We expect the mean of the composite image quality score for ventilator-gated images to be approximately 25.62, which is the expected upper limit of the self-gated image quality

score. The margin of 1.75 was derived using an expected mean of 24.75 for the self-gated image (~4% reduction in image quality score compared to that achieved with the ventilator-gated method). The non-inferiority comparison will be a one-sided test at a 0.025 level of statistical significance and a -1.75 margin. A sample size of 36 will achieve a statistical power of greater than 90% to detect non-inferiority between ventilator-gated and self-gated MUSIC-MRI using a one-sided t-test with a non-inferiority margin of -1.75 and a true difference of zero with a standard deviation of 3.0 and a significance level of 2.5%. Taking into account missing data due to unusable image quality or incomplete studies, we plan to enroll 40 CHD subjects.

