	
The primary efficacy endpoint is the sum of diagnostic image quality scores (i.e. the composite score) from the 7 pre-identified anatomical structures. A parametric two-sided t-test will be used to compare the Feraheme® group and the Ablavar® group where both groups will use ventilator-gated MUSIC-MRI. This comparison will be a two-sided test at the 0.05 level of significance. A formal interim analysis for the image quality will be performed when 20 CHD subjects in each group have completed the image acquisition. The interim analysis will be prepared by an independent statistician and presented only to the independent DMC who will make recommendations about the ongoing conduct of the study. Two hypotheses will be used to preserve the overall type 1 error rate of 0.05 between this single interim analysis and the final analysis of the mean differences in the composite image quality scores. A two-sample t-test will be used to compare the Feraheme®-enhanced and the Ablavar®-enhanced groups for the primary analysis at the 0.025 level of significance.
 
Part II: Diagnostic efficacy study to compare self-gated MUSIC-MRI with ventilator-gated MUSIC-MRI in 40 children
 
Control = Contrast agent from Part I + ventilator-gated MUSIC-MRI
 
Test = Contrast agent from Part I + self-gated MUSIC-MRI
 
Part II will start after results from Part I are available. The superior contrast agent as determined by Part I of the study or in the case that statistical significance is not achieved in Part I, the appropriate contrast agent in consultation with the DMC will be used for Part II. The primary efficacy endpoint is the composite image quality score from the 7 pre-identified anatomical structures. A parametric two-sided paired t-test will be used to compare the ventilator-gated MUSIC-MRI and self-gated MUSIC-MRI groups. The quality of the self-gated MUSIC-MRI images is expected to be not much worse than those from ventilator-gated MUSIC-MRI images. This comparison of non-inferiority will be a one-sided test at the 0.025 level of significance with a -1.75 margin in the composite image quality score.
 
SECONDARY EFFICACY ENDPOINTS:

--	---

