7.2 Study Design Part I: diagnostic efficacy of Feraheme vs. Ablavar

For Part I of our study, the legal guardian(s) of all consecutive pediatric patients with suspected or known CHD referred for cardiovascular MRI will be given the option of having their child undergoing an Ablavar®-enhanced MRI or a Feraheme®-enhanced MRI, after the potential benefits and risks of both agents are clearly explained and their questions addressed. The risks and benefits of using each of these agents will be verbally discussed with the patients' legal guardians and referring cardiologists or cardiac surgeons. A copy of the written IRB-approved informed consent will be provided. Because Feraheme®-based imaging is in use at several pediatric specialty centers, including UCLA whereby Feraheme is used more frequently than GBCA-based imaging for children in our study age-group, in the current state of professional equipoise, we judge it appropriate to allow parents to participate in the choice of agent (see Section 11.1.1 for detailed justification). Those choosing to undergo an Ablavar®-enhanced MRI will be considered the "control" group while those choosing to undergo a Feraheme®-enhanced MRI will be considered enrolled in the "test" group. We plan to recruit 40 patients for test group and 40 patients for the control group with consideration of approximately 10% missing or unusable image quality. To avoid performing a study with larger-than-necessary enrollment, the Investigators will request an interim analysis at 50% enrollment for both groups. If statistical analyses, either as part of interim analyses requested by the Investigators, or after full enrollment, shows statistically significant primary endpoint comparison, we will close Part I enrollment and begin Part II enrollment using the superior agent identified in Part I. If statistical significance is not reached for the primary endpoint during interim analyses, the patient enrollment for both test and control groups will continue until full enrollment, at which time another final statistical analyses will be performed with $p < 0.025$ considered statistically significant. If statistical significance is not reached at full enrollment, we will seek advice from the DMC regarding Part II of the study, including contrast agent to be used.

See Section 11.1.1 for justification for involving the patient's parents in patient group assignment.

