18 STATISTICAL METHODS AND CONSIDERATIONS

The primary efficacy analysis of visual imaging quality will be conducted using all usable scans from the patients. All safety analyses will be conducted using a population defined as all patients undergoing study contrast-agent (Safety Population).

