[Interim Analyses]: To avoid performing a study with larger-than-necessary enrollment for Part I of our study, a formal interim analysis for the composite imaging score will be performed at approximately 20 CHD subjects for each of the contrast group (50% of the target number for the primary analysis). Alpha-spending for the interim analyses and the primary analysis will be 0.025 and 0.025 (both two-sided), respectively. The overall alpha for the composite image quality score will be preserved at the two-sided 0.05 significance level. The interim analysis of the composite image quality score will be conducted by an independent statistician under the charter of the DMC.

The interim effect of Feraheme compared to the Ablavar of ventilator-gated MUSIC-MRI based on the average composite score from two image readers will be tested with a two group t-test with an appropriate transformation if needed. Non-parametric Wilcoxon rank sum test will be considered if the data are not normally distributed based on the Shapiro-Wilk and Shapiro-Francia tests and transformation is not feasible.

18.4.2 Part II – Difference in the composite image quality score between ventilator-gated and self-gated MUSIC-MRI

The primary efficacy endpoint for Part II is the composite image quality score defined in 18.4.1. Data will be tested for normality using the Shapiro-Wilk and Shapiro-Francia tests. The composite subjective image quality score will be compared between ventilator-gated MUSIC-MRI and the self-gated MUSIC-MRI using a paired t-test with appropriate transformation if needed. If the data are not normally distributed and transformation is not possible, a Wilcoxon-sign-rank test will be considered. The null hypothesis is that the mean difference in the image quality scores of the self-gated images is smaller than or equal to the mean from ventilator-gated images with the non-inferiority margin of -1.75 (self-ventilator ≤ -1.75). The alternative hypothesis is that the mean difference in image quality score of self-gated images from the ventilator-gated images is greater than the non-inferiority margin of -1.75 (self-ventilator > -1.75) (see the detail of choosing the margin in section 18.7.2.).

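### The 62% interim power in Part I assumes 20 analysed scores per group, but the interim is triggered by subject counts; with the plan's own 10% loss it is about 57%, or 57% to 62% under the synopsis trigger.

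*Combined protocol and SAP*

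**What the plan says.** **Interim power.** Section 18.7.1 says that "a sample size of 20 in each contrast agent group will achieve a power of 62"%, for a composite-score difference of 1.75 and "with an estimated standard deviation of 2.10 in each group and a significance level of 2.5"%. Section 18.4.1 fixes the level: "Alpha-spending for the interim analyses and the primary analysis will be 0.025 and 0.025 (both two-sided), respectively". It also says that the interim effect "will be tested with a two group t-test with an appropriate transformation if needed".

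**Interim trigger.** It is worded in three ways, each a count of subjects:
- 50% enrolment in both groups, that is 20 of 40 each (synopsis, Planned Interim Analyses; section 7.2).
- Approximately 20 subjects per group, described as half the target (18.4.1).
- In the synopsis, Statistics, Part I: "A formal interim analysis for the image quality will be performed when 20 CHD subjects in each group have completed the image acquisition".

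**Analysis set and loss.** Section 18 says the primary efficacy analysis "will be conducted using all usable scans from the patients". Section 7.2 sets 40 per group "with consideration of approximately 10% missing or unusable image quality". Section 18.7.1 powers the final analysis on 36 per group and enrols 40, to cover unusable image quality and incomplete studies. Section 15.3 replaces only subjects who withdraw before the required images are recorded.

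**The concern.** The two power statements in section 18.7.1 stand on different bases. The final one uses the number left after loss (36 of 40). The interim one uses the number before loss (20 of 40). If the plan's loss rate also holds over the first half of enrolment, fewer than 20 scores per group reach the interim test.

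Sections 7.2 and 18.4.1 give the purpose of the interim as avoiding a larger enrolment than necessary. The 62% is the plan's only figure for how likely the interim is to achieve that, assuming the planned difference is true. An overstated figure gives the DMC and IRB too favourable a view of the chance of stopping early.

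**Working it through.** **Inputs.** Difference d = 1.75, SD s = 2.10 in each group, interim n = 20 and final n = 36 per group (all 18.7.1); two-sided level 0.025 and two-group t-test (18.4.1); loss about 10% (7.2). Equal groups are assumed.

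**Formula.** With n per group, df = 2n − 2 and noncentrality λ = d / (s·√(2/n)). Power is the probability that a noncentral t variable with df and λ falls beyond ±c, where c is the 0.9875 quantile of the central t distribution.

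**Step 1: reproduce the plan's figures.**
- n = 20: df = 38, λ = 1.75 / (2.10 × √0.1) = 2.635, c = 2.334, power 62.0%. This matches the stated 62%. A normal approximation gives 65.3% and a one-sided 0.025 t-test gives 72.9%, so the 62% is the two-sided t-test on 20 analysed scores, with no loss allowance inside it.
- n = 36: 89.1% by the t-test, 90.2% by the normal approximation, against the stated 90%.
- 36 / 0.9 = 40, the planned enrolment per group. The final analysis therefore carries the 10% allowance.

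**Step 2: apply the same loss at the interim.** 20 × 0.9 = 18.

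| Analysed per group | λ | Power |
|---|---|---|
| 20 | 2.635 | 62.0% |
| 19 | 2.569 | 59.4% |
| 18 | 2.500 | 56.6% |

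The fall from 20 to 18 is 62.0 − 56.6 = 5.4 points. If each scan is lost independently with probability 10%, the expected power is 56.4%, so the result does not depend on losing exactly two per group.

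**Step 3: match the loss to each trigger.**
- *50% enrolment:* missing and unusable scans both come out of the 20. About 18 are analysed and power is about 57%.
- *Completed acquisition:* incomplete acquisitions do not count towards the 20, so only the unusable share of the 10% is lost. The documents do not split the 10%. Analysed n lies between 18 and 20, and power between 57% and 62%.
- *Approximately 20 subjects:* the count is loose, but the wording contains no allowance for loss.

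**Step 4: effect on Part I as a whole.** In 100,000 simulated trials per scenario, testing at two-sided 0.025 at the interim and again at 36 per group, the probability of rejecting at either look was 90.1% with 18 per group at the interim and 90.1% with 20. The 0.025 + 0.025 split limits type I error to 0.05 whatever the interim n.

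**Step 5: size of the alternative trigger.** 20 / 0.9 = 22.2, so 23 imaged per group are needed to expect 20 usable; 22 would give 22 × 0.9 = 19.8.

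**The case against.** **The stated number is right.** A reader might infer a calculation error in the 62%. The documents do not support that: it reproduces exactly at n = 20. The fault is a mismatch between the sample assumed and the sample the design supplies.

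**The loss may be smaller than 10%.** A reader might take 57% as the true power under every trigger. The documents do not support that either. The synopsis Statistics wording already excludes incomplete acquisitions. Section 18.3 scores a non-diagnostic structure as 1, with a composite floor of 7, so some poor scans may be scored rather than dropped. Section 15.3 replaces early withdrawals. These points stand, and they are why the answer under that trigger is a range. They do not remove the concern: a recorded but unusable scan is not replaced, and the 50%-enrolment wording appears in two places.

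**The gap is small beside other uncertainty.** The pilot SD was 1.82 (Feraheme group) against the planned 2.10. With 1.82 and n = 18, power would be 70.4%. At n = 20, an SD of 2.22 instead of 2.10 would bring power down to 56.7%, much the same drop. This is fair as to importance, but the plan chose 2.10 and its power statement should hold on its own inputs.

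**Nothing else depends on the 62%.** This stands. A reader might infer that Part I is underpowered or that its type I error is inflated by this mismatch; step 4 of the working shows neither.

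**Conclusion.** The point holds as a minor one. The 62% describes 20 analysed scores per group, which the design does not secure under its own loss assumption. The overstatement is about 5.4 points under the 50%-enrolment trigger, and between 0 and 5.4 points under the completed-acquisition trigger.

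This rests on the plan's difference and SD, on the approximate 10% applying evenly over enrolment, and on equal groups at the interim. Agent choice rests largely with parents and both groups must reach the count, so the faster group could exceed 20, which would raise power somewhat.

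**What to change.** **Preferred:** restate interim power in section 18.7.1 as about 57% at 18 usable scans per group. Eighteen is half of the 36 on which the final analysis is powered, so the look stays at the intended 50% point. The cost is one figure.

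**Alternative:** trigger the interim at 20 usable, scored scans per group, about 23 imaged. This secures the 62% but moves the look about three patients per group later, to 20/36 = 56% of the powered final sample.

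**In either case:** use one trigger wording in the synopsis (Planned Interim Analyses and Statistics), 7.2, 18.4.1 and 18.7.1, and say what makes a scan unusable rather than scored at the floor. Target enrolment of 80, the tests and the alpha levels do not change.

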19 DATA COLLECTION, RETENTION AND MONITORING

19.1 Data Collection Instruments

The Investigator will prepare and maintain adequate and accurate source documents designed to record all observations and other pertinent data for each subject treated with the study drug.

Study personnel will enter data from source documents corresponding to a subject's visit into the protocol-specific electronic Case Report Form (eCRF) when the information corresponding to that visit is available. Subjects will not be identified by name in the study database or on any study documents to be collected by the Sponsor (or designee), but will be identified by a subject number and initials.

If a correction is required for an eCRF, the time and date stamps track the person entering or updating eCRF data and create an electronic audit trail.

The Investigators are responsible for all information collected on subjects enrolled in this study. All data collected during the course of this study must be reviewed and verified for completeness and accuracy by the Investigators. A copy of the eCRF will remain at the Investigators' site at the completion of the study.

19.2 Data Management Procedures

The data will be entered into a validated database. The Data Management group will be responsible for data processing, in accordance with procedural documentation. Database lock will occur once quality assurance procedures have been completed.

All procedures for the handling and analysis of data will be conducted using good computing practices meeting FDA guidelines for the handling and analysis of data for clinical trials.

19.3 Data Quality Control and Reporting

After data have been entered into the study database, a system of computerized data validation checks will be implemented and applied to the database on a regular basis. All changes to the study database will be documented.

19.4 Archival of Data

The database is safeguarded against unauthorized access by established security procedures; appropriate backup copies of the database and related software files will be maintained. Databases are backed up by the database administrator in conjunction with any updates or changes to the database.

At critical junctures of the protocol (e.g., production of interim reports and final reports), data for analysis is locked and cleaned per established procedures.

19.5 Availability and Retention of Investigational Records

The Investigators will make study data accessible to the monitor, other authorized representatives of the Sponsor (or designee), IRB, and Regulatory Agency (e.g., FDA) inspectors upon request. A file for each subject will be maintained that includes the signed Informed Consent, HIPAA Authorization and copies of all source documentation related to that subject. The Investigators will ensure the reliability and availability of source documents from which the information on the CRF was derived.

All study documents (patient files, signed informed consent forms, copies of CRFs, Study File Notebook, etc.) will be kept secured for two years after the center has been notified that the IND has been discontinued. There may be other circumstances for which the Sponsor is required to maintain study records and, therefore, the Sponsor will be contacted prior to removing study records for any reason.

19.6 Monitoring

Monitoring visits will be conducted by representatives of the Sponsor according to the U.S. CFR Title 21 Parts 50, 56, and 312 and ICH Guidelines for GCP (E6). By signing this protocol, the Investigator grants permission to the Sponsor (or designee), and appropriate regulatory authorities to conduct on-site monitoring and/or auditing of all appropriate study documentation.

19.7 Subject Confidentiality

In order to maintain subject confidentiality, only a subject number and subject initials will identify all study subjects on CRFs and other documentation submitted to the Sponsor. Additional subject confidentiality issues (if applicable) are covered in the Clinical Study Agreement.

20 ADMINISTRATIVE, ETHICAL, REGULATORY CONSIDERATIONS

The study will be conducted according to the Declaration of Helsinki, Protection of Human Volunteers (21 CFR 50), Institutional Review Boards (21 CFR 56), and Obligations of Clinical Investigators (21 CFR 312).

Any serious, unexpected suspected adverse reactions, findings from other clinical, animal, or in-vitro studies that suggest significant human risk, and any clinically important increases in the rate of a serious suspected adverse reaction will be sent to the FDA, Division of Medical Imaging Products, and to all investigators no later than 15 calendar days after determining that the information qualifies for reporting [21 CFR 312.32(c)(1)]. Additionally, any unexpected fatal or life-threatening suspected adverse reaction will be reported to the FDA Division of Medical Imaging Products no later than 7 calendar days after initial receipt of the information [21 CFR 312.32(c)(2)]. Each submission will be addressed to the Regulatory Project Manager and/or the Chief, Project Management Staff for the Division.

To maintain confidentiality, all reports, evaluation forms, and other records will be identified by a coded number and initials only. All study records will be kept in a locked file cabinet and code sheets linking a patient's name to a patient identification number will be stored separately in

another locked file cabinet. Clinical information will not be released without written permission of the subject, except as necessary for monitoring by the FDA. The Investigator must also comply with all applicable privacy regulations (e.g., Health Insurance Portability and Accountability Act of 1996, EU Data Protection Directive 95/46/EC).

20.1 Protocol Amendments

Any amendment to the protocol will be written by the Investigators. Protocol amendments cannot be implemented without prior written IRB approval except as necessary to eliminate immediate safety hazards to patients. A protocol amendment intended to eliminate an apparent immediate hazard to patients may be implemented immediately, provided the IRBs are notified within five working days.

